4.9 Overdose

There is no specific antidote for cytarabine overdose. Cessation of therapy followed by management of ensuing bone marrow depression including whole blood or platelet transfusion and antibiotics as required. Twelve doses of 4.5 g/m2 by IV infusion over one hour every 12 hours induces irreversible and fatal central nervous system toxicity.

Cytarabine may be removed by haemodialysis.

5. Pharmacological properties

5.1 Pharmacodynamic properties

Cytarabine (ARA-C) is metabolised *in vivo* to ARA-CTP phosphorylated compound. This competitively inhibits DNA polymerase and may also inhibit certain acid kinase enzymes. Primarily the drug acts as a false nucleoside and competes for enzymes involved in the conversion of cytidine nucleotide to deoxycytidine nucleotide and also incorporation into the DNA.

Cytarabine has no effect on non proliferating cells nor on proliferating cells unless in the S phase. It is a cell cycle specific antineoplastic drug.

5.2 Pharmacokinetic properties

Oral administration is ineffective due to rapid deamination in the gut. Cytidine deaminase is concentrated in the liver and intravenous doses show biphasic elimination with half lifes of approximately 10 minutes and 1-3 hours.

After 24 hours 80% of a dose has been eliminated either as the inactive metabolite or as the unchanged cytarabine, mostly in urine but some in bile.

CSF levels of 50% of plasma levels are achieved with intravenous infusion. Intrathecal dosing results in slower elimination (T1/2 2-11 hours).

Cytarabine is rapidly and widely distributed into tissues, crosses the blood brain barrier and also the placenta.

5.3 Preclinical safety data

There is no pre-clinical data of relevance to the prescriber which are additional to that already included in other sections of the SPC.

6. Pharmaceutical particulars

6.1 List of excipients

Sodium Chloride Water for Injections

6.2 Incompatibilities

Solutions of cytarabine have been reported to be incompatible with various drugs, i.e. carbenicillin sodium, cephalothin sodium, fluorouracil, gentamicin sulphate, heparin sodium, hydrocortisone sodium succinate, insulin-regular, methylprednisolone sodium succinate, nafacillin sodium, oxacillin sodium, penicillin G sodium. However, the incompatibility depends on several factors (e.g. concentrations of the drug, specific diluents used, resulting pH, temperature). Specialised references should be consulted for specific compatibility information.

6.3 Shelf life

Before use: 12 months.

In use: Chemical and physical in-use stability has been demonstrated for 7 days at room temperature. From a microbiological point of view, the product should be used immediately. If not used immediately, in-use storage times and conditions prior to use are the responsibility of the user and would normally not be longer than 24 hours at 2-8°C, unless dilution has taken place in controlled and validated aseptic conditions.

6.4 Special precautions for storage

Do not store above 25°C. Keep container in the outer carton .

6.5 Nature and contents of container

Clear Type I glass vials, rubber stopper.

Clear Type I Onco-Tain® Vials, rubber stopper.

Pack sizes 5's, 25's and 50's.

Not all presentations and pack sizes may be marketed.

6.6 Special precautions for disposal and other handling

Not applicable.

7. Marketing authorisation holder

Hospira UK Ltd [name] United Kingdom.

8. Marketing authorisation number(s)

PL 04515/0040

9. Date of first authorisation/renewal of the authorisation
7th July 1992/10th October 2006
10. Date of revision of the text
June 2015

APPENDIX 2 - INCLUSION AND RANDOMIZATION PROCESS

(NB screening shot are corresponding to protocol version dated 21/01/2013)

Connect to www.graspa-ml.com and choose "patients" section, then "new patient"

Enter patient data selection and validate

PATIENT DATA

Before filling the "Patient data" section, please be sure to enter accurate information (particularly Date of birth).

Patient N°:	1004-07 (as reference for all further correspondences)	
Patient Initials:	Last name: (2 1 st letters)	Only if authorized
Date of birth:		
Sex:	Omale OFemale	
Date of bone marrow sample for exploratory assessments:		
	Validate	0

Answer inclusion exclusion criteria and validate

RANDOMIZATION / SCREENING FAILURE

Before filling the "Randomization / Screening Failure" section, please be sure to have all required information, Otherwise, you can close this window,

INCLUSION CRITERIA		
	Yes	No
1- Patient over 65 years old and less than 85 years old	0	0
 Newly diagnosed Acute Myeloid Leukemia (AML) or post myelodysplastic syndrome diagnosed in the 6 months prior study enrollment 	0	0
 Unfit for intensive chemotherapy (at risk to suffer treatment related pejorative toxicities /early death) or patient unwilling to receive intensive chemotherapy 	0	c
4- WHO performance status \leq 2 and estimated life expectancy \geq 3 months	0	0
5- Eligible to receive low-dose cytarabine treatment	0	0
6- Evidence of post-menopausal status for female (absence of menstruation for 12 months)	0	0
7- Subscription to social security insurance	0	0
8- Provision of written Informed Consent	0	0

	Yes	No
1- Patients with M3 AML of FAB classification (APL, Acute Promyelocytic Leukemia))	0	0
2- Patients with AML involving chromosome 16 abnormalities or translocation (8:21) (CBF-AML)	0	0
3- History of grade 3-4 pancreatitis or grade 3-4 thromboembolic event (according NCI-CTCAE Version 4.0)	0	0

Appendix 3: Samples preparation for centralized analyses

Amino acids: asparagine, aspartate, glutamine, and glutamate - At D11, D13, D18 and D27 of chemotherapy course

Procedure:

One sample of 4mL of blood should be taken and immediately refrigerated (put in an iced water bath)

Centrifuge the blood sample no later than 15 minutes after sampling, at 800-1,000 G and at 4°C for 10 minutes

Harvest the serum and process the sample

Add \geq 100 µL (1 part) 10% sulfosalicylic acid to \geq 400 µL (4parts) of serum to precipitate proteins, mix thoroughly (vortex mixer) and centrifuge 5 minutes at 2,500 G at 4°C

Fill the supernatant into a propylene tube and freeze between $\leq -20^{\circ}$ C and -80° C, store at this temperature until shipping.

Samples will be transferred on dry ice for analysis to:

SGS Cephac [name], France

Whole blood asparaginase - At D11, D13, D18 and D27 of chemotherapy course

Procedure:

Two sample of 2mL of blood should be taken and freeze between $\leq -20^{\circ}$ C and -80° C; store at this temperature until shipping.

Samples will be transferred on dry ice for analysis to:

SGS Cephac [name], France

Immunogenicity: Anti-L-asparaginase antibodies - At D11 each course of chemotherapy, before GRASPA administration

Procedure:

One sample of 2mL of blood should be taken

Centrifuge the blood sample no later than 15 minutes after sampling, at 800-1,000 G and 4°C for 15 minutes

Fill the supernatant into 2 propylene tubes and freeze between \leq -20°C and -80°C, store at this temperature until shipping.

Samples will be transferred on dry ice for analysis to:

CHU Hôtel Dieu

Laboratoire d'immunologie biologie

[name]

[name] (France)

Biomarker assessments on bone marrow aspirate of patients.

Procedure

Two Bone marrow samples will be collected as follows:

-2 mL will be collected in EDTA tube (for culturing cells after ficoll separation)

-2 mL will be collected in PAXgene tube (for extraction of RNA)

Patient samples will be transferred (ambient temperature) for analysis to

ERYTECH Pharma - R& D department

[name]

[name] (France)

Fax the Analysis Form to trigger pick-up of samples to ship Fax No: [name] (CEMO)

Dosage and Central Laboratories

Analysis	Reference for measurement	Central Laboratory	Responsible

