3.2 L-asparaginase in AML treatment

L-asparaginase activity is based on its catalytic activity for degrading asparagine and glutamine in blood and tissue liquids into aspartic and glutamic acid and ammonia, which thus induce a cytotoxic response against asparagine-dependent tumors. Survival and growth of most of leukemic cells, such as lymphoblasts as well as certain solid cancer cell lines, are asparagine-dependent, using this amino acid as nutriment for protein synthesis. This degradation is mainly evidenced by their asparagine depletion levels. This asparagine depletion results in a regression of leukemic cell proliferation (Broome, 1981) by several mechanisms involved in the destruction of tumor cells following treatment: inhibition of protein biosynthesis and subsequently, induction of apoptosis (Story, 1993).

Conversely, normal cells are resistant to L-asparaginase as they can synthesize asparagine using asparagine synthetase (ASNS) from other amino acids (glutamine or aspartic acid) when the level of serum asparagine is lowered. However some cancer cells are lacking ASNS and therefore when they are deprived of L-asparagine for growth and DNA replication, they become apoptotic and die.

A potential interest in AML has been identified from therapeutic use of free L-asparaginase and some bibliographic data. It has been demonstrated that AML blasts, especially M5 subtype cells, display a low level of ASNS (Codegoni 1995; Dubbers 2000; Kaspers 1999 Zwaan 2000). Kitoh *et al.* (1996) performed immunocytochemical staining in AML samples and showed that FAB M1, M4 and M5 cells were negative for ASNS. This supports the results of Okada *et al.* (2003) showing the relative sensitivity of M1, M4 and M5 cells to L-asparaginase and strongly suggests that ASNS expression is inversely correlated with sensitivity to L-asparaginase in AML cells.

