4.2 Secondary objectives

- Response to treatment
- Progression-free survival
- Relapse Free Survival
- Patient transfusion needs
- Patients Quality of life evolution
- Number of hospitalizations
- Safety of GRASPA in combination with cytarabine
- Pharmacokinetic and pharmacodynamic parameters of GRASPA
- Immunogenicity of GRASPA
- Asparagine Synthetase (ASNS) expression and sensitivity to L-asparaginase in bone marrow cells (optional)
- Biomarker cytogenetic testing (optional)

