4.3.2 Secondary endpoints

- Percentage of patients with Complete remission (CR), Complete remission with incomplete recovery (neutrophil or platelet regeneration, CRi), Partial remission (PR)
- Progression-free survival (PFS) defined as the time elapsed between randomization and resistant disease or relapse or death from any cause
- Relapse Free Survival defined only for patients who achieved CR or CRi as the time elapsed between date of CR/CRi and date of disease relapse or death from any cause
- Percentage of patients who need transfusions (red blood cells and/or platelets), number of transfusions by patient
- Patient quality of life evaluated using the EORTC QLQ-C30 version 3 scale
- Number of hospitalizations (except scheduled protocol visit) required during the study
- Safety of GRASPA in combination with low-dose cytarabine, with specific attention to :
 - o Grade 3 or 4 of Pancreatic toxicity
 - o Grade 3 or 4 of hepatic toxicity, allergic reaction or coagulation event
 - o Grade 3 or 4 of hypoproteinemia or hyperglycemia/diabetes
 - All other non-hematologic Grade 4 toxicities

(*NB* grading reference used: NCI CTCAE version 4.0)

- Pharmacokinetic and pharmacodynamic parameters:
 - o Plasma concentrations of asparagine, aspartate, glutamine, glutamate
 - Whole Blood L-asparaginase activity
- Immunogenicity by measuring titer of anti-L-asparaginase antibodies
- Biomarker cytogenetic testing (optional)
- Measurement of the following parameters on harvested bone marrow tumor cells (optional):
 - Asparagine synthetase protein expression
 - Asparagine synthetase mRNA expression
 - In vitro sensitivity to L-asparaginase

(See also section 8.8 for details)

Table 3 hereafter provides the definitions of response criteria in AML.

Category	Definition
Complete remission (CR)*	Bone marrow blasts < 5%; absence of blasts with Auer rods; absence of extramedullary disease; absolute neutrophil count > $1.0 \times 10^{9}/L$ (1000/µL); platelet count > $100 \times 10^{9}/L$ (100 000/µL); red blood cell transfusion independence
CR with incomplete recovery (CRi)	All CR criteria except for residual neutropenia ($< 1.0 \times 10^{9}/L [1000/\mu L]$) or thrombocytopenia ($< 100 \times 10^{9}/L [100 000/\mu L]$)
Partial remission (PR)	all hematologic criteria of CR; decrease of bone marrow blast percentage to 5% to 25%; and decrease of pre-treatment bone marrow blast percentage by at least 50%

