5.6.3. Exploratory Endpoints

Bone marrow biopsy/aspirate will be collected at study entry and analyzed for biomarker analysis of potentially relevant biomarkers, utilizing proteomic and transcriptomic techniques. Assessments could be repeated on further bone marrow aspirate, if possible. This data will be for exploratory purposes.

The following assays will be performed:

- Mononuclear cells from bone marrow of AML patients will be assessed for Asparagine synthetase (ASNS) expression by two different methods: real-time qRT-PCR for the quantification of ASNS mRNA and westernblot for the quantification of ASNS.
- Mutational analyses and detection of gene amplification of relevant oncogenes; e.g. *FLT3*, *NPM1*, *IDH*, or *KIT*.
- Dependent upon tissue availability, immunohistochemistry (IHC), gene expression profiling and transcriptomic profiling may be performed.
- Other biomarkers deemed relevant that may emerge with new scientific data.

Cells isolated from bone marrow by ficoll will be also cultured in presence of L-asparaginase. *In-vitro* sensitivity to L-asparaginase will be assessed at ERYTECH Pharma by measuring the cytotoxicity using a colorimetric assay.

ARN and proteic extraction obtained from samples will be frozen at ERYTECH Pharma in order to perform other analyses allowing a better knowledge of mechanism of action, or new drug development.

ASNS mRNA expression at baseline will be summarized by treatment group, and select efficacy endpoints will be plotted against ASNS mRNA expression.

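### The plan names different cell sources for ASNS mRNA and plots efficacy against it without adjusting for marrow blast percentage, which the reading may partly track

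*Protocol*

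**What the plan says.** The documents describe the material for this measurement in four places.

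- **Protocol 4.2 (objective):** "Asparagine Synthetase (ASNS) expression and sensitivity to L-asparaginase in bone marrow cells (optional"). This does not restrict the material to tumour cells.
- **Protocol 4.3.2 (endpoint):** "Measurement of the following parameters on harvested bone marrow tumor cells (optional"). ASNS protein, ASNS mRNA and in vitro sensitivity all fall under this line.
- **Protocol Appendix 3 (sampling):** "Two Bone marrow samples will be collected as follows". The first is "2 mL will be collected in EDTA tube (for culturing cells after ficoll separation"). The second is "2 mL will be collected in PAXgene tube (for extraction of RNA"). The second tube is the only RNA source listed, and no separation step is given for it.
- **SAP 5.6.3 (analysis):** "Mononuclear cells from bone marrow of AML patients will be assessed for Asparagine synthetase (ASNS) expression by two different methods: real-time qRT-PCR" and western blot.

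SAP 5.6.3 then summarises baseline ASNS mRNA by arm and states that "select efficacy endpoints will be plotted against ASNS mRNA expression". It mentions no blast term. SAP 5.2.4 plans no covariate adjustment in general. The adjusted Cox model in SAP 5.6.1 uses performance status strata, age and karyotype. Baseline marrow blast percentage is collected (Protocol 8.6 and 8.10), but in the SAP's treatment-effect analyses it serves only as a subgroup factor (5.2.6: below 20%, 20 to 30%, above 30%).

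**The concern.** Blast ASNS is the quantity of biological interest. Protocol 3.2 argues that AML blasts carry little of it, whereas "normal cells are resistant to L-asparaginase as they can synthesize asparagine using asparagine synthetase". In any sample that contains both kinds of cell, the measured level depends on how much ASNS the blasts make and also on what share of the sample is blasts.

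The SAP's own blast groups show that this share is expected to vary and may be low. If blast burden is also related to outcome, a plot of outcome against the unadjusted reading can show a trend that blast burden alone produces, or can hide a real one. At stake is how ASNS is read as a marker of who benefits. SAP 5.6.3 singles out ASNS mRNA for a plot against efficacy, and ASNS is central to the case for asparaginase in AML.

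**Working it through.** The documents give no figure for this point, so there is none to reproduce. The check has a textual part and a numerical part.

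**1. Cell source.** The endpoint says tumour cells, the objective says marrow cells, the SAP says mononuclear cells, and the sampling appendix gives a marrow tube with no separation step. These are different materials for one measurement. That conflict needs no assumption.

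**2. Mixture arithmetic.** Let *b* be the blast fraction of the sample and *r* the ratio of blast ASNS to normal-cell ASNS, with normal-cell ASNS set to 1. The reading is

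*m* = *b* × *r* + (1 − *b*).

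No document gives *r*, so a range is shown.

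| *r* (assumed) | *m* at 20% blasts | *m* at 90% blasts | 20% reading ÷ 90% reading |
|---|---|---|---|
| 0.1 | 0.82 | 0.19 | 4.3 |
| 0.2 | 0.84 | 0.28 | 3.0 |
| 0.5 | 0.90 | 0.55 | 1.6 |
| 1 | 1.00 | 1.00 | 1.0 |
| 2 | 1.20 | 1.90 | 0.63 (reversed) |

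Each row holds blast biology constant, so the spread comes from blast percentage alone.

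**3. How well the reading represents blast ASNS.** Assume *b* is uniform on 20% to 95% and *r* is log-normal (median 0.4, log SD 0.7). As a further assumption, let Ficoll remove 60% of non-blast cells, so that the blast fraction becomes *b* / (*b* + 0.4 × (1 − *b*)). Correlations use the log of the reading.

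| Reading | With true blast ASNS | With blast percentage |
|---|---|---|
| Whole marrow | 0.74 | −0.52 |
| Whole marrow, blast-percentage trend removed | 0.87 | 0 by construction |
| Ficoll-separated, unadjusted | 0.86 | −0.40 |

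Separation improves the measurement but leaves most of the dependence on blast percentage.

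**4. Spurious association with OS.** This simulation used 123 patients and 1,500 runs. Blasts were uniform on 20% to 90%, the log SD of ASNS was 0.3 or 0.6 in blasts and 0.2 in normal cells, and there was no censoring. The hazard of death doubled from 20% to 90% blasts, and ASNS had no effect on OS. The table gives the share of runs in which the rank correlation of the reading with OS was significant at 5%.

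| Median blast-to-normal ratio | Whole marrow | Ficoll-separated (60% of non-blasts removed) |
|---|---|---|
| 0.25 | 26–36% | 21–34% |
| 0.5 | 13–20% | 10–17% |
| 1.0 | about 5% | about 5% |

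After adjustment for blast percentage, the mean partial rank correlation of the whole-marrow reading with OS was between −0.003 and 0.005 in every scenario. The adjustment removes the artefact; a change of cell source alone does not.

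**The case against.** There is a substantial case on the other side, and much of it stands.

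- **The unseparated source is inferred.** Appendix 3 does not name ASNS next to the PAXgene tube, and Protocol 8.9 lists other possible uses of RNA. The appendix is not a full map of assays to tubes, since it names no sample for the western blot. The lab manual is not available and the central-laboratory table is cut off; either could add a step. This stands, so the source is put here as an appearance.
- **The assays need not disagree.** A reader might infer that mRNA, western blot and in vitro sensitivity will conflict because their samples are handled differently. SAP 5.6.3 assigns mononuclear cells to both expression methods in one sentence. Trusting it for protein while overriding it for mRNA would be selective, so the documents do not support that inference.
- **The size is assumed.** Protocol 3.2 describes what normal cells can do when serum asparagine falls. It does not give a baseline marrow mRNA level. A patient with few, ASNS-low blasts would read high only if the ratio is below 1. This stands.
- **The use is exploratory.** The endpoint is optional, and the output is a summary and plots with no test, cut-off or decision rule. A purely prognostic blast effect would appear in both randomised arms and need not imitate a treatment-by-ASNS effect; the simulation covers association with OS only. This stands and limits the consequence.

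None of this removes the conflicting descriptions or supplies the missing blast term. A mononuclear sample also contains non-blast cells, so the adjustment is needed even if the SAP's description is the true one.

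**Conclusion.** The point holds as a matter of consistency and of exploratory analysis. The documents name different material for ASNS mRNA, and the planned plots take no account of blast percentage. With an assumed blast-to-normal ratio of 0.1 to 0.5, blast percentage alone moves the reading 4.3-fold to 1.6-fold between 20% and 90% blasts. At a ratio of 1 the effect vanishes, and above 1 it reverses. The false-association rates also assume that blast burden affects survival.

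A reader might go further and conclude that the trial certainly measures whole-marrow ASNS, or that its test of mechanism is invalid. The documents do not support either conclusion. The handling is not fully visible, and under the assumptions in step 3 the unadjusted reading still correlates 0.74 with true blast ASNS. The analyses of OS, PFS and response are unaffected.

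**What to change.** **In SAP 5.6.3:** adjust every summary or plot of ASNS mRNA against efficacy for baseline marrow blast percentage, whatever the cell source. Use it as a covariate, or stratify by the blast groups in SAP 5.2.6. A continuous covariate does more, because the top group is wide: at a ratio of 0.2 the reading still falls from 0.76 at 30% blasts to 0.28 at 90% (0.76 / 0.28 = 2.7-fold). Label values from PAXgene tubes as whole-marrow ASNS, and do not pool them with values from separated cells.

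**Across Protocol 4.2, 4.3.2, Appendix 3 and SAP 5.6.3:** state one cell source for ASNS mRNA, checked against the lab manual.

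**Cost:** wording and one covariate that is already recorded, settled before database lock. No new samples are needed.

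**Optional:** taking RNA from the Ficoll-separated cells is only a partial remedy. It is probably too late as well: the samples are taken at study entry, and SAP 3.1 refers to the end of recruitment in the past tense. It would leave fewer cells for culture, and RNA integrity would need checking because Appendix 3 ships samples at ambient temperature.

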Appendix 4: EORTC-QLQ-C30_V3

EORTC QLQ-C30 (version 3)

We are interested in some things about you and your health. Please answer all of the questions yourself by circling the number that best applies to you. There are no "right" or "wrong" answers. The information that you provide will remain strictly confidential.

Please fill in your initials:	
Your birthdate (Day, Month, Year):	
Today's date (Day, Month, Year):	31

		Not at All	A Little	Quite a Bit	Very Much
1.	Do you have any trouble doing strenuous activities, like carrying a heavy shopping bag or a suitcase?	1	2	3	4
2.	Do you have any trouble taking a long walk?	1	2	3	4
3.	Do you have any trouble taking a short walk outside of the house?	1	2	3	4
4.	Do you need to stay in bed or a chair during the day?	1	2	3	4
5.	Do you need help with eating, dressing, washing yourself or using the toilet?	1	2	3	4
Du	ring the past week:	Not at All	A Little	Quite a Bit	Very Much
6.	Were you limited in doing either your work or other daily activities?	1	2	3	4
7.	Were you limited in pursuing your hobbies or other leisure time activities?	1	2	3	4
8.	Were you short of breath?	1	2	3	4
9.	Have you had pain?	1	2	3	4
10.	Did you need to rest?	1	2	3	4
11.	Have you had trouble sleeping?	1	2	3	4
12.	Have you felt weak?	1	2	3	4
13.	Have you lacked appetite?	1	2	3	4
14.	Have you felt nauseated?	1	2	3	4
15.	Have you vomited?	1	2	3	4
16.	Have you been constipated?	1	2	3	4

Please go on to the next page

During the past week:	Not at All	A Little	Quite a Bit	Very Much
17. Have you had diarrhea?	1	2	3	4
18. Were you tired?	1	2	3	4
19. Did pain interfere with your daily activities?	1	2	3	4
20. Have you had difficulty in concentrating on thing like reading a newspaper or watching television?	s, 1	2	3	4
21. Did you feel tense?	1	2	3	4
22. Did you worry?	1	2	3	4
23. Did you feel irritable?	1	2	3	4
24. Did you feel depressed?	1	2	3	4
25. Have you had difficulty remembering things?	1	2	3	4
26. Has your physical condition or medical treatment interfered with your family life?	1	2	3	4
27. Has your physical condition or medical treatment interfered with your social activities?	1	2	3	4
28. Has your physical condition or medical treatment caused you financial difficulties?	1	2	3	4

For the following questions please circle the number between 1 and 7 that best applies to you

29.	How would you rate your overall health during the past week?							
	1	2	3	4	5	6	7	
Ver	y poor						Excellent	
30.	30. How would you rate your overall quality of life during the past week?							
	1	2	3	4	5	6	7	
Ver	y poor						Excellent	

GRASPA-AML 2012-01

Protocol Version 07, dated 05 Oct 2015

- CONFIDENTIAL -

